9.3 STATISTICAL ANALYSES

9.3.1 GENERAL APPROACH

All data will be deidentified before analysis. Due to the small sample size, the analysis will consist of descriptive statistics, as defined in terms of means, standard deviations, and percentile ranks where applicable.

9.3.2 ANALYSIS OF THE PRIMARY ENDPOINT

To identify potential barriers in recruiting patients/parents for a larger-scale clinical trial to evaluate the effectiveness of the DB, questions in the parent-reported surveys will ask about the parents' perspectives regarding joining a future study. The enrollment log will also include patients who do not wish to participate in the study and their reason(s) for refusal/withdrawal. Descriptive statistics will be used to analyze the recruitment rate, dropout rate, and related responses on the parent-reported survey for the intent to treat population, the experimental arm population, and the control arm population.

The enrollment log will also record the age and fit issues of patients that do not adequately fit the available prototype but are otherwise eligible. This will serve to inform future adaptations of the new DB for future trials.

9.3.3 ANALYSIS OF THE SECONDARY ENDPOINTS

Parent-reported comfort levels will be determined by parent-reported surveys with 5-point Likert scale responses. Results from these surveys will be analyzed with descriptive statistics for the intent to treat population, the brace discomfort population, and the brace comfort population.

Daily bracing times will be measured by a temperature sensor added in each patient's boots for the entire 90-day study period. The number of hours the brace is worn per day will be divided by the standard number of desirable hours in brace (12 hours) in order to obtain a fraction that quantifies the patient's adherence to the FAB. Mean 'adherence fractions' will be calculated for patients in each arm, and then compared using descriptive statistics. This analysis will be performed for the intent to treat population, the brace discomfort population, and the brace comfort population. This data will be compared to the self-reported brace wear hours by parents in their daily logs.

To ensure minimal efficacy of the DB prototype, all signs of clubfoot recurrence will be carefully examined at each study visit. The null hypothesis is that 'the dynamic bar does not lead to higher rates

of clubfoot recurrence,' and it will be rejected if the number of patients in the safety population that develop clubfoot recurrence during the 90-day study period, is substantially greater in the experimental arm than it is in the control arm (i.e. more than 2 instances of clubfoot recurrence in the experimental arm than in the control arm). Note that this endpoint is not intended to prove safety or efficacy, but rather to ensure that the design may prevent early recurrence before a larger-scale trial is conducted. Clubfoot recurrence is defined as a Pirani score > 0.5, a new occurrence of cavus, adduction and/or hindfoot varus, or a loss of passive ankle dorsiflexion (equinus) of < 10 degrees above neutral or a reduction of 5 or more degrees from the previous visit. Note that all clinical tests required to diagnose recurrence are routinely performed as standard clubfoot care.

If consent is provided by the parents, a member of the study team will also record a video of each patient wearing their prescribed bar on Day 30 of the study period. These videos will be closely studied to compare the range of motion provided by the SB to the DB, and to verify that the DB consistently maintains proper foot position during use. Videos will be recorded on a password-protected personal device, audio will be removed, then the video will be uploaded each day to the patient's REDCap forms. The video will then be deleted from the personal device. All efforts will be made to made to only include the patient's feet and legs in the field of the video, and to blur or remove any identifiable physical marks like unique birthmarks and tattoos on the patient's skin.

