1 PROTOCOL SUMMARY

1.1 SYNOPSIS

Title:	Development and Evaluation of Novel Dynamic Bar for Foot Abduction
	Brace for Clubfoot Treatment
Study Description:	This is an assessor-blinded randomized feasibility trial assessing the feasibility of conducting a large-scale clinical trial to evaluate the effectiveness of a new dynamic bar for foot abduction bracing for clubfoot treatment. Feasibility will be determined by the ability to recruit patients within the goal study period and to retain participants. Eligible patients must have a well-corrected idiopathic clubfoot (Pirani Score ≤ 0.5) and be in the minimum 12 hours per day bracing stage of the Ponseti clubfoot treatment protocol. The overall study period will be 90 days in length. For the first 30 days, the experimental cohort will wear the new Dynamic Bar (DB) with standard ankle-foot orthoses (boots) and the control cohort will continue wearing their Standard Bar (SB). After this 30-day period, the experimental cohort will return to wearing their SB.
	All patients will be evaluated on Day 0, Day 7, Day 30, and Day 90 of the study period to monitor for recurrence of the clubfoot deformity, complications of brace wearing, to submit brace wear logs, and to complete parent-reported questionnaires regarding their perceptions of the Foot Abduction Brace (FAB) and their child's comfort. A minimum of 10 patients per arm will be recruited. A temperature sensor will be added in each participant's boots during the 90-day study period to objectively measure time of brace wear. It is hypothesized that when patients are wearing the DB, they will experience higher brace tolerance defined as increased wear time of the brace as measured by the temperature sensors, and higher comfort levels as reported by parents, without an increase in clubfoot deformity recurrence compared to the SB. Most patient health information will be collected and stored in the SickKids Clubfoot Research Registry (REB #1000053919).
Objectives:	Primary Objective: To evaluate the ease of recruiting and retaining participants for a randomized-controlled effectiveness trial of a novel FAB bar.

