3 OBJECTIVES AND ENDPOINTS

OBJECTIVES	ENDPOINTS	JUSTIFICATION FOR ENDPOINTS	
Primary			
To evaluate the ease of recruiting and retaining	Recruitment rate, dropout rate, and related responses on	This informs on the potential barriers to recruitment and	
participants for a randomized- controlled effectiveness trial of a novel FAB bar.	the parent-reported survey.	scale clinical trial to evaluate the effectiveness of the DB.	
Secondary			
1) To compare parental perception of the child's comfort in the SB versus the DB for foot abduction bracing in Ponseti clubfoot treatment.	1) Patient comfort levels determined by parent- reported surveys with 5-point Likert scale responses completed at Day 0, Day 30, and Day 90 of the study period.	1) Child comfort in brace is critical to achieving full brace compliance. As our study subjects are aged 1-3 years and unable to complete surveys or communicate their experience, parent-proxy reported outcome measures are a validated method to use as an endpoint (13, 14).	
2) To compare patient tolerance of the SB to the DB as measured by parent self-reporting and by how many hours the brace is worn per day as recorded by temperature sensors placed in the boots.	2) Daily brace wear hours as measured by a parent self- reported log and by temperature sensors implanted inside the boots.	2) Brace non-compliance is the leading cause of clubfoot recurrence. Therefore, increasing brace tolerance decreases clubfoot recurrence and leads to improved clinical outcomes.	
3) To perform a preliminary assessment of the effectiveness of the DB at preventing clubfoot recurrence during the bracing phase when the brace is worn as prescribed for a 30-day trial period.	3) Presence of clubfoot recurrence defined as a Pirani score > 0.5 representing any new development of cavus, adduction and/or hindfoot varus, or a loss of passive ankle dorsiflexion (equinus) of < 10 degrees above neutral or a reduction of 5 or more degrees from the previous visit.	3) While there is no validated definition for clubfoot recurrence, our clinical endpoints are commonly used criteria in other clubfoot studies. Since this is a feasibility study with only 20 participants, safety and efficacy cannot be clinically proven but we want to ensure the design at least prevents early relapse during the night-time bracing phase before the DB is produced at-large.	

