6.4 STUDY INTERVENTION COMPLIANCE

Standard care for clubfoot treatment is to assess bracing compliance by asking the parent about the patient's daily wear time at each scheduled appointment. Studies have shown that parents over-report brace wear by approximately 30% (12). To objectively measure brace compliance, a temperature sensor will be added in each patient's boots during the 90-day study period. Measurements obtained from these sensors will be used in the analysis of the 2nd secondary endpoint to compare brace wear time in the SB versus the DB. We will compare these results with parent self-reported logs of brace wear.

The temperature sensors that will be used are the DS1921G-F5 Thermochron iButtons, designed and manufactured by iButtonLink Technology in Wisconsin, USA. Each device is a battery powered data logger equipped with a temperature sensor. The devices will be set to record the temperature of the boots' insoles every 45 minutes and launched on Day 0 and Day 30 on the study period. The device complies with medical standards and is calibrated against a National Institute of Standards and Technology (NIST) traceable source (18). Thermochron iButtons have previously been used in a similar clubfoot bracing adherence study (19). The data obtained from these temperature sensors will be used to calculate the daily brace wear time of each patient during the interventions, by measuring the temperature increase when the child is in the brace.

For unilateral clubfoot cases, the temperature sensor will be placed in the boot that holds the clubfoot. For bilateral cases, the sensor will be placed on the right boot. To implant each sensor, technicians at SickKids will drill a hole through the sole of the boot and insert the iButton with an interference fit. This hole will be located directly over top of the slider in the "Quick Clip" mechanism, so that the slider secures the sensor and prevents it from falling out. The insole of the boot will be then covered with a layer of ShearBan[®] in order to ensure patient comfort and to ensure that the temperature sensor never comes into contact with skin. ShearBan is a self-adhesive film often used in insoles and orthopaedic braces (20). This procedure mimics that of another clubfoot brace compliance study, for which an installation video has been created (21).

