8 STUDY ASSESSMENTS AND PROCEDURES

8.1 ASSESSMENTS

The physical exam that will be performed at each study visit will be done according to standard care for clubfoot. The only physical assessments that are not part of standard clubfoot care is measuring the patients' tibia length to ensure appropriate fit of the DB, as well as measuring the patients' height and weight to explore any possible reasons for bar malfunction or breakage. The height and weight of each participant will be measured and recorded by the blinded outcome assessor, with or without help of the clinic nurse, who routinely collects this data at SickKids.

To quantify parent perception and feedback, three different surveys will be administered to the parents/caregiver at scheduled times throughout the trial. This includes a survey at Day 0, Day 30, and Day 90 of the study period. Surveys will be completed in-person at the time of clinic visits, or via email after the visit if there was insufficient time to collect the data.

The purpose of the first survey on Day 0 is to assess parental perception of the SB prior to the study period. For the experimental arm, the second survey will assess parental perception of the new DB immediately after 30 days of wear, and the third survey will assess parental impression of returning to the SB after use of the DB at Day 90. For the control arm, the Day 30 and 90 surveys will serve as a test-retest reliability measure from Day 0 to assess if any variation over time (due to change in foot shape, treatment, recurrence, or environment) can be detected.

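### Section 9.3.3 compares brace wear by arm without restricting the comparison to Day 0 to the Day 30 visit, the only period in which the arms wear different bars

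*Combined protocol and SAP*

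**What the plan says.** Secondary objective 2 (section 3) is "To compare patient tolerance of the SB to the DB as measured by parent self-reporting" and by sensor-recorded hours per day. Its endpoint, "Daily brace wear hours as measured by a parent" log and by the boot sensors, names no period. The comfort endpoint in the same table is tied to Day 0, Day 30 and Day 90. For the experimental arm, section 8.1 adds that "the second survey will assess parental perception of the new DB immediately after 30 days of wear".

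Under sections 1.1 and 4.1 the experimental arm wears the DB for 30 days and then the SB for 60. The control arm wears the SB throughout.

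The only analysis of wear is in section 9.3.3. A sensor sits in each patient's "boots for the entire 90-day study period". Daily hours are divided by 12 to give an adherence fraction, and mean fractions "will be calculated for patients in each arm, and then compared using descriptive statistics". The section gives no window, no split at Day 30 and no comparison by bar. The parent log is to be set against the sensor data, also without a period.

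Other sections show what is intended. Section 6.4 says the sensor data serve the "2nd secondary endpoint to compare brace wear time in the SB versus the DB". The synopsis hypothesis is that "when patients are wearing the DB, they will experience higher brace tolerance". Section 4.2 announces comparisons both between arms and within experimental-arm patients. On logistics, the sensors are "launched on Day 0 and Day 30 on the study period" (section 6.4) and read at Day 30 and Day 90, and the logs are collected on the same two days (section 4.1).

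**The concern.** The target is a contrast between two bars, but the written analysis is a contrast between two arms over an unspecified period. After Day 30 the arms wear the same bar. A by-arm mean over every recorded day therefore mixes DB days and SB days in the experimental arm, and it estimates the bar contrast only if nearly all of the DB effect persists after the bar is taken away.

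The within-patient comparison promised in section 4.2 has no method in section 9.3.3. The order is always DB then SB, so a raw before-and-after difference cannot be separated from a change over time.

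If the window is left open, it will be chosen after the wear data have been seen. Section 10.1.6 declares that the investigators invented the bar. Blinded clinical assessment, the safeguard named there, does not settle an analysis window.

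**Working it through.** **Plan's own figures.** The documents state no target difference, SD, carry-over or power for brace wear, so there is nothing to reproduce for this endpoint. The only powered figure is 62 per arm for recurrence in the future trial (section 9.1). With 30% versus 10%, 80% power and 5% type 1 error (two-sided assumed), [1.96 × √(2 × 0.2 × 0.8) + 0.842 × √(0.21 + 0.09)]² / 0.2² = 61.6, which rounds up to 62. It reproduces and does not depend on wear.

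**Inputs from the documents.**
- DB days 30, then SB days 60 (sections 1.1 and 4.1).
- Visit 3 at Day 30 ± 7 and Visit 4 at Day 90 ± 7 (section 1.3).
- Denominator 12 hours (section 9.3.3).
- 10 per arm (section 9.1).

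**Assumed.** D is the DB effect on wear in hours per day while the DB is worn. The share p of D persists after the return to the SB.

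**1. Dilution if all days are averaged.** The arm difference is (30D + 60pD)/90 = D × (30 + 60p)/90.

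| p | Factor |
|---|---|
| -0.5 | 0 |
| 0 | 0.33 |
| 0.5 | 0.67 |
| 0.7 | 0.80 |
| 1 | 1.00 |

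For illustration, D = 1 hour per day is 1/12 = 0.083 on the adherence fraction up to Day 30. Over 90 days with p = 0 it is 0.33 hours, or 0.028. A negative p means that wear falls below control after the return to the SB.

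**2. Share of SB days in the experimental arm's record.** On schedule this is 60/90 = 67%. If the bar changes at Visit 3, opposite extremes of the visit windows give 1 - 37/83 = 55% and 1 - 23/97 = 76% for one participant. If the bar changes exactly at Day 30, the range is 1 - 30/83 = 64% to 1 - 30/97 = 69%.

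**3. Within-patient comparison.** Let T be the change over time common to both arms, taken as first period minus second. The experimental arm's change is (1 - p)D + T and the control arm's change is T. The raw change therefore contains T. Subtracting the control change leaves (1 - p)D, which is 1.0, 0.5 and 0 times D at p = 0, 0.5 and 1.

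**4. Precision given up with a 30-day mean.** Let r be day-to-day SD divided by between-child SD (assumed 1 to 3). With independent days, the ratio of the standard error of an arm mean, 30 versus 90 days, is √[(1 + r²/30)/(1 + r²/90)].
- r = 1: 1.011
- r = 2: 1.042
- r = 3: 1.087

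The 90-day mean has the better signal-to-noise only if (1 + 2p)/3 exceeds 1/ratio, that is, if p exceeds (3/ratio - 1)/2. This gives p above 0.98, 0.94 and 0.88.

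If days are instead correlated with an assumed lag-1 correlation of 0.5, r² is multiplied by 3 - 4/30 = 2.87 in the 30-day term and by 3 - 4/90 = 2.96 in the 90-day term. The ratios become 1.03, 1.11 and 1.20, and the thresholds for p become 0.96, 0.86 and 0.75.

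**The case against.** The strongest reply is that nothing in the plan orders pooling. The reference to 90 days describes how long the sensor stays in the boot, not the averaging period. Section 6.4 says the data are for comparing the two bars and speaks of wear during the interventions. A competent analyst would split at Day 30, because the data arrive that way. Section 9.3.3 gives no time points for comfort either. The endpoint is secondary and untested, so one clarifying clause would do.

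Part of this stands. Pooling is a reading, not a stated rule, and the dilution applies only under that reading. The wording about interventions does not settle the window, however, because the synopsis counts 90 days of the SB as the control intervention. The comfort endpoint does get its time points in sections 3 and 8.1, whereas no section gives the wear analysis a window. One clause would also leave the within-patient comparison of section 4.2 without a method.

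Three qualifications of the figures stand as well:
- A rebound below control wear (p < 0) is possible and would make the dilution worse.
- Correlated days raise the precision cost above 1% to 9%. In the example above it reaches 20%, which does not reverse the recommendation unless carry-over is high.
- The 55% to 76% range assumes that the bar changes at Visit 3. If it changes at Day 30 and the visit falls on Day 37, the first window would include 7 SB days out of 37 (19%).

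**Conclusion.** The concern holds. The only wear analysis in the plan is a by-arm mean with no window, in a design where the arms wear different bars for one third of the scheduled record. The intent to compare bars is clear, but section 9.3.3 does not turn it into an analysis.

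If all days are averaged, the stated contrast shrinks to between one third and all of its size for p between 0 and 1, and it stays below 80% unless p is at least 0.70. Neither p nor D is in the documents, so the size is conditional; the omission itself is not.

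The consequence is limited. No test or error rate is involved, and 10 children per arm give an imprecise estimate either way. But a descriptive estimate is all that objective 2 will yield, so it should estimate the right quantity. This should be corrected before the wear data are examined.

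**What to change.** Amend section 9.3.3 as follows.

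1. Define the between-arm wear comparison as the mean adherence fraction from Day 0 to the actual Day 30 visit date, by assigned arm.
2. Report Day 30 to Day 90 separately, by arm.
3. Give the within-patient comparison of section 4.2 as the experimental arm's change between the two periods beside the control arm's change over the same periods, and note that carry-over would shrink it.
4. Split the parent log in the same way.

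Participants who return early to the SB stay in their assigned arm, consistent with sections 7.1 and 7.2, and are listed with the date where it is recorded. Means and SDs suffice under section 9.3.1. The SAP should also state how the date of the bar change relates to the Day 30 visit. The 30 days in section 4.1, the one-month maximum in section 4.2 and a visit window reaching Day 37 have to be reconciled on this.

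The cost is a few sentences and slightly more descriptive output; items 1 to 4 need no new data. The list of early returns is the exception. Section 8.2.5 requires onset dates for adverse events, but no section explicitly requires the date of a return to the SB, so the list is limited to recorded dates unless a field is added. The 30-day mean is also somewhat noisier, by 1% to 9% in the standard error of an arm mean if days are independent and more if they are correlated.

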2.3 RISK/BENEFIT ASSESSMENT

This DB has the potential to greatly improve patient and parent experience with clubfoot bracing during the night-time phase of treatment. By increasing the patient's independent leg motion and comfort, brace tolerance should improve, and in turn, reduce the risk of relapse. By increasing brace wear, brace comfort and minimizing recurrence, this new bar design should lead to improved clinical outcomes, as well as patient and parent-reported outcomes.

The risks associated with the use of the DB prototypes includes all the risks associated with SBs, such as pressure sores and skin rashes. Additional risks associated with the DB might include bar malfunction or breakage, due to lack of extensive material evaluations. Clubfoot recurrence still occurs with the SB, but the risk may be increased with the DB as it will give patients unprecedented mobility. Walking in any foot abduction brace is not recommended, however the added mobility provided by the DB might enable safer mobility for the child possibly preventing injury and falls. To mitigate risks and complications, a blinded outcomes assessor will regularly evaluate the patients, and if any sign of clubfoot recurrence is observed, the child will immediately return to their original FAB with serial casting

as needed. The intervention period in this feasibility study is purposely short to avoid placing a child in a potentially ineffective brace for a prolonged period of time.

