8.2.4 CLASSIFICATION OF AN ADVERSE EVENT

8.2.4.1 SEVERITY OF EVENT

The severity of an AE will be assessed by a blinded outcomes assessor, physiotherapist [name], and/or the PI. They will use the following definitions when assessing the intensity of an AE:

- Mild Events require minimal or no treatment and do not interfere with the participant's daily activities.
- **Moderate** Events result in a low level of inconvenience or concern with the therapeutic measures. Moderate events may cause some interference with functioning.

• Severe – Events interrupt a participant's usual daily activity and may require systemic drug therapy or other treatment. Severe events are usually potentially life-threatening or incapacitating. Of note, the term "severe" does not necessarily equate to "serious".

The only "severe" AE that is foreseen to potentially occur during the study is clubfoot recurrence. Clubfoot recurrence would likely be treated by serial casting, as is standard care for clubfoot treatment. Mild to moderate AEs may potentially include pressure sores, skin rashes, and unintentional selfinjuries. All of these AEs are known risks associated with FABs.

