9.2 POPULATIONS FOR ANALYSES

The following study populations are defined and will be analyzed as specified below:

- Intent to treat population: the total population of patients registered in the study.
- Experimental arm population: all registered participants in the experimental arm with DB.
- Control arm population: all registered participants in the control arm with SB.

- Safety population: all registered participants who wore their FAB as prescribed for the full 90-day study period.
- Brace discomfort population: all registered participants who have any history of brace intolerance or indicated in the parent-reported survey that they are not comfortable/have concerns with their original FAB.
- Brace comfort population: all registered participants who have no history of brace intolerance and indicated in the parent-reported survey that they are comfortable/have no concerns with their original FAB.

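### The recurrence rule counts only children braced as prescribed for all 90 days, so a child casted for recurrence found at Day 7 or Day 30 drops out of the count

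*Combined protocol and SAP*

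**What the plan says.** Section 9.3.3 states a null hypothesis that the DB does not lead to more recurrence. It is to be "rejected if the number of patients in the safety population that develop clubfoot recurrence during the 90-day study period" shows a clear excess with the DB, spelled out as "more than 2 instances of clubfoot recurrence in the experimental arm than in the control arm".

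Section 9.2 defines the set in which recurrences are counted: "Safety population: all registered participants who wore their FAB as prescribed for the full 90-day study period". It also defines a wider set: "Intent to treat population: the total population of patients registered in the study". Section 9.3.3 uses the wider set for comfort and for wear time ("This analysis will be performed for the intent to treat population, the brace discomfort population, and the brace comfort population"), but not for recurrence.

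On management, section 2.3 says that "if any sign of clubfoot recurrence is observed, the child will immediately return to their original FAB with serial casting" as needed. Section 8.2.4.1 adds: "Clubfoot recurrence would likely be treated by serial casting, as is standard care for clubfoot treatment". The schedule in 1.3 places examinations after baseline at Days 7, 30 and 90. The DB is worn for the first 30 days only.

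**The concern.** Membership of the counting set depends on what happens after the event. A child whose recurrence is found at Day 7 or Day 30 and treated by casting stops wearing the brace, fails the 90-day wear condition, and is removed together with the recurrence. Recurrences first found at Day 90 are not lost this way. The status of a DB child moved back early to the standard bar (SB) without casting is unclear, since the definition refers to the FAB and not to the bar.

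The recurrences most exposed to loss are those found at the two visits that cover DB wear, and sections 2.3 and 8.2.3 themselves raise a possibly higher recurrence risk with the DB. The rule is the plan's only pre-stated recurrence criterion before a larger trial, and as written it can miss the excess it is meant to flag.

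**Working it through.** **Plan's own figure.** The 9.3.3 rule has no stated error rate or power, so there is nothing to reproduce for it. The one powered figure in 9.1, 62 per arm for the future trial, does reproduce (two-sided 5%, 80% power, 30% v 10%, no continuity correction), but it does not bear on this point.

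**Who is counted**
1. The rule counts recurrences in the safety population (9.3.3).
2. Membership requires the FAB worn as prescribed for all 90 days (9.2).
3. Recurrence leads to casting as needed (2.3), which is likely (8.2.4.1).
4. A casted foot cannot wear the boot. This is a clinical inference; the documents do not state it.
5. So a child casted before Day 90 fails the membership condition, and no text adds that child back.

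**Direct examples, with no assumed rates.** The rule is met when DB count minus control count is at least 3.
- All randomised: 4 − 1 = 3, met. One DB child casted before Day 90 and the control child not casted: 3 − 1 = 2, not met.
- All randomised: 3 − 0 = 3, met. One DB child casted: 2 − 0 = 2, not met.

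**Chance of meeting the rule.** Inputs: 10 per arm (9.1); assumed 90-day risks pD (DB) and pS (control); and c, the share of recurrences lost, which is the share found before Day 90 times the chance of casting. The documents give none of pD, pS or c, so ranges are shown.

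The formula is P(X − Y ≥ 3), with X ~ Bin(10, pD(1 − c)) and Y ~ Bin(10, pS(1 − c)), independent. Children without recurrence do not matter, because the rule compares counts.

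Worked case, pD = 0.30, pS = 0.05, c = 0. Sum P(Y = y) × P(X ≥ y + 3):

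0.5987 × 0.6172 + 0.3151 × 0.3504 + 0.0746 × 0.1503 + 0.0105 × 0.0473 = 0.3695 + 0.1104 + 0.0112 + 0.0005 = 0.492

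| Assumed risk, DB v control | c = 0 | c = 25% | c = 50% | c = 75% |
|---|---|---|---|---|
| 30% v 5% | 49% | 32% | 15% | 3% |
| 40% v 10% | 61% | 44% | 23% | 6% |
| 20% v 5% | 23% | 14% | 6% | 1% |

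If half of DB recurrences but no control recurrences are lost, at 30% v 5%, then X ~ Bin(10, 0.15), Y ~ Bin(10, 0.05) and the chance is 12%.

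**Equal true risks.** At 10% in both arms: 3.0% with all counted, 0.7% with half lost. At 30% in both arms: 11.0% and 5.6%.

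**The case against.** - **Other sections keep such children.** Section 7.1 says that stopping a bar is not leaving the study. Section 7.2 invokes intention to treat for children who do not follow the schedule and keeps the data of withdrawn participants. These are general rules. Section 9.3.3 names a specific, narrower population for recurrence, and the general wording does not change it.
- **Following prescribed casting could count as wearing the brace as prescribed.** The phrase is undefined, so the reading is possible. But the definition refers to wearing the FAB for the full 90 days, and time in a cast does not naturally fit that. If this is what the sponsor means, it should be written.
- **Objective 3 concerns the brace worn as prescribed.** It does, but for a 30-day trial period. That supports separating poor wearers. It does not support removing a child who wore the brace properly until recurrence was found.
- **Little hangs on the rule.** This stands in large part. The analysis is descriptive (9.3.1), and 9.3.3 itself says: "Note that this endpoint is not intended to prove safety or efficacy". No section ties an action to the rule; suspension under 10.1.1 rests on separate judgement. Recurrences are documented as adverse events (8.2.5), notified to the safety board and the ethics board (6.3), and open to the safety board's by-arm review (10.1.4). These limit the harm but do not correct the count.
- **The assumed risks are high.** This is fair. The 20–41% in 2.2 and 9.1 has no 90-day horizon, and 4.2 expects little chance of finding a difference. At 10% v 5% the rule is met 4.6% of the time with nothing lost and 0.9% with half lost; at 5% v 2% it is met 1.0% of the time even with nothing lost. The table shows what is lost if the DB does raise recurrence markedly, which is the case the rule exists to flag.

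**Conclusion.** The concern holds. As written, a child casted for recurrence before Day 90 is removed from the recurrence count because of that recurrence, and a single removal can turn a met rule into an unmet one. This rests on the wording of 9.2 and 9.3.3 plus the clinical inference that a cast precludes the boot. The size depends on risks and loss shares that the documents do not give. If half of recurrences are lost, the chance of meeting the rule falls by roughly two thirds to three quarters across the tabulated cases (61% to 23%, 49% to 15%, 23% to 6%). Because the events stay on the safety record and the endpoint is preliminary, this should be corrected but does not undermine the trial's primary feasibility aim.

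**What to change.** 1. **Section 9.3.3.** Replace the safety population in the rule with: *among all randomised children, by randomised arm, counted once at the first visit at which a criterion below is met, whatever the later casting, bar change or wear, unless the parent asks that the data not be used*.
2. **Section 9.2.** Rename the safety population the *as-prescribed set* and judge wear up to the earlier of first recurrence or Day 30, to match objective 3. Use it for a supportive table beside the main count. A child casted or returned early to the SB because of recurrence then stays in the set if wear was as prescribed until that point. State the wear threshold and the recurrence window for this table, as the plan gives no threshold now.

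Section 2.3 needs no change.

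**Cost.** Wording in two sections and one table; no new visit, examination or data item. There are two downsides. The main count will include recurrences due to poor wear, which is why the as-prescribed table stays. The rule will also be met more often when true risks are equal: 3.0% against 0.7% at 10% risk, and 11.0% against 5.6% at 30% risk, if half of recurrences would otherwise be casted out. That is about a fourfold and a twofold rise. Replacement of participants under 7.2 can make arm sizes unequal, which affects a raw-count rule now as well, so report the denominators beside the counts.
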